### ***Significant Nonserious Adverse Events***

A significant nonserious AE is a device-related, non-sight threatening adverse event that warrants discontinuation of any contact lens wear for greater than or equal to 2 weeks. In addition, the investigator must report any occurrences of the following as a significant nonserious adverse event:

- Peripheral nonprogressive noninfectious ulcers
- All symptomatic corneal infiltrative events

Corneal staining score greater than or equal to grade 3 (Refer to MOP for grading scales)

- Temporary vision loss as defined by loss of 2 or more lines of BCVA from baseline visit that persists for 2 or more weeks

Neovascularization score greater than or equal to grade 2 (Refer to MOP for grading scales)

*The above events are based on the categories provided in the ISO 11980 and the US FDA Premarket Notification (510[k]) Guidance Document for Daily Wear Contact Lenses and Contact Lens Care Products.*

### **Device Deficiencies**

A device deficiency is an inadequacy of a medical device with respect to its identity, quality, durability, reliability, safety, or performance. A device deficiency may or may not be associated with patient harm (i.e., ADE or SADE); however, not all ADEs or SADEs are due to a device deficiency. The investigator should determine the applicable category listed in the device deficiency eCRF for the identified or suspect device deficiency and report any patient harm separately. Examples of device deficiencies include the following:

- Failure to meet product specifications (e.g., incorrect lens power/diameter/base curve/color)
- Lens/solution cloudy
- Lens surface/edge defect
- Torn lens during handling/in pack
- Packaging deficit (e.g., mislabeled product, tampered seal, leaking bottle/container)
- Suspect product contamination

## **11.2 Monitoring for Adverse Events**

At each visit, after the subject has had the opportunity to spontaneously mention any problems, the investigator should inquire about AEs by asking the standard questions shown below and report as applicable:

- "Have you had any health problems since your last study visit?"
- "Have there been any changes in the medicines you take because of a new health issue since your last study visit?"

In addition, changes in *any protocol-specific parameters* [REDACTED] evaluated during the study are to be reviewed by the investigator. Any untoward (unfavorable and unintended) change in *a protocol-specific parameter* [REDACTED] that is clinically relevant, in the opinion of the investigator, is to be reported as an AE. These clinically relevant changes will be reported regardless of causality.

### 11.3 Procedures for Recording and Reporting

AEs are collected from the time of signing of informed consent. Any preexisting medical conditions or signs/symptoms present in a subject prior to the start of the study (i.e., before informed consent is signed) are not considered AEs in the study and should be recorded in the medical history section of the eCRF.

In addition, temporary lens awareness or visual changes during the fitting process are not considered AEs if the investigator assesses that the symptom(s) can reasonably resolve within the anticipated adaptation period.

For each recorded event, the ADE/SAE documentation must include: the date of occurrence, severity, treatment (if applicable), outcome, and assessments of the seriousness and causality. In addition, the investigator must document all device deficiencies reported or observed with test and comparator products on the device deficiency eCRF. The site must submit all available information on ADEs, SAEs, and device deficiencies to the study sponsor immediately as follows:

- ADEs or SAEs are documented on the *Serious Adverse Event and Adverse Device Effect* eCRF within 24 hours of the investigator's or site's awareness.
- Device deficiencies are documented on the *Device Deficiency* eCRF within 24 hours of the investigator's or site's awareness.  
A printed copy of the completed serious adverse event and adverse device effect and/or device deficiency eCRF must be included with product returns, if applicable.
- Additional relevant information after initial reporting must be entered into the eCRF as soon as the data become available.
- Document any changes to concomitant medications on the appropriate eCRFs.
- Document all relevant information from discharge summary, autopsy report, certificate of death etc., if applicable, in narrative section of the *Serious Adverse Event and Adverse Device Effect* eCRF.

*Note:* Should the EDC system become nonoperational, the site must complete the appropriate paper *Serious Adverse Event and Adverse Device Effect* and/or *Device Deficiency* form. The completed form is emailed to the study sponsor at [[contact]](mailto:[contact]) according to the timelines outlined above; however, the reported information must be entered into the EDC system once it becomes operational.

In addition to recording all AEs into the EDC system, any AEs and device deficiencies for nonstudy marketed devices/products (i.e., CLEAR CARE® Cleaning & Disinfecting Solution used concomitantly during the study will be considered and processed as

spontaneous following the postmarket vigilance procedures) and should be communicated to the device's/product's manufacturer as per local requirements.

**Study sponsor representatives may be contacted for any protocol related question and their contact information is provided in the manual of procedures that accompanies this protocol.**

*Note, depending upon the nature of the AE or device deficiency being reported, the study sponsor may request copies of applicable portions of the subject's medical records. The investigator must also report all AEs and device deficiencies that could have led to a SADE according to the requirements of regulatory authorities or IRB/IEC.*

### **Intensity and Causality Assessments**

Where appropriate, the investigator must assess the intensity (severity) of the AE based on medical judgment with consideration of any subjective symptom(s), as defined below:

#### ***Intensity (Severity)***

Mild	An AE is mild if the subject is aware of but can easily tolerate the sign or symptom.
Moderate	An AE is moderate if the sign or symptom results in discomfort significant enough to cause interference with the subject's usual activities.
Severe	An AE is severe if the sign or symptom is incapacitating and results in the subject's inability to work or engage in their usual activities.

For every AE in the study, the investigator must assess the causality (related or not related to the medical device or study procedure). An assessment of causality will also be performed by study sponsor utilizing the same definitions, as shown below:

#### ***Causality***

Related	An AE classified as related may be either definitely related or possibly related where a direct cause and effect relationship with the medical device or study procedure has not been demonstrated, but there is a reasonable possibility that the AE was caused by the medical device or study procedure.
Not Related	An AE classified as not related may either be definitely unrelated or simply unlikely to be related (i.e., there are other more likely causes for the AE).

The study sponsor will assess the AEs and may upgrade the investigator's assessment of seriousness and/or causality. The study sponsor will notify the investigator of any AEs that are upgraded from nonserious to serious or from unrelated to related.

## **11.4 Return Product Analysis**

Study sponsor representatives and their contact information are provided in the MOP that accompanies this protocol.

Alcon study products associated with device deficiencies and/or product related AEs should be returned and must include the complaint # which will be provided by study sponsor after the case is entered in the study sponsor's Global Product Complaint Management System (GPCMS).

## **11.5 Unmasking of the Study Treatment**

Masked information on the identity of the assigned medical device should not be disclosed during the study. [REDACTED] If the treatment assignment needs to be unmasked in the interest of subject safety, the investigator is encouraged to contact an appropriate study sponsor representative prior to unmasking the information if there is sufficient time. Dependent upon the individual circumstances (i.e., medical emergency), the treatment may be unmasked prior to contact with the study sponsor. The study sponsor must be informed of all cases in which the masking was broken and of the circumstances involved. Additionally, the study sponsor may be required to unmask the information in order to fulfill expedited regulatory reporting requirements.

## **11.6 Follow-up of Subjects with Adverse Events**

The investigator is responsible for adequate and safe medical care of subjects during the study and for ensuring that appropriate medical care and relevant follow-up procedures are maintained after the study.

The investigator should provide the study sponsor with any new safety information (which includes new AEs and changes to previously reported AEs) that may affect the safety evaluation of the device. For AEs that are unresolved/ongoing at time of discontinuation, any additional information received at follow-up should be documented in the eCRFs up to study completion (i.e., database lock). Any additional data received up to 3 months after subject has completed the study should be documented and available upon the study sponsor's request.

All complaints received after this time period will be considered and processed as spontaneous (following the postmarket vigilance procedures) and should be communicated to the medical device's manufacturer as per local requirements. The investigator should also report complaints on non-Alcon products directly to the manufacturer as per the manufacturer's instructions or local regulatory requirements.

[figure not shown]
## **11.7 Pregnancy in the Clinical Study**

Women who are pregnant (as stated by the subject) at the time of study entry are excluded from participation. However, pregnancy should be included in the corresponding eCRF if a woman becomes pregnant (as stated by the subject) during the study. Pregnancy is not reportable as an AE; however, complications may be reportable and will be decided on a case-by-case basis. Subjects who become pregnant during the study will not be discontinued; however, data will be excluded from the effectiveness analysis because pregnancy can alter refraction and VA results.

## **12 ANALYSIS PLAN**

Continuous variables will be summarized using the number of observations, mean, standard deviation (SD), median, minimum, and maximum, as well as confidence intervals (CIs) or confidence limits (CLs) where applicable. Categorical variables will be summarized with frequencies and percentages from each category.

Any deviations to the analysis plan will be updated during the course of the study as part of a protocol amendment or will be detailed in the clinical study report.

### **12.1 Subject Evaluability**

Final subject evaluability must be determined prior to breaking the code for masked treatment assignment and locking the database, based upon the data evaluability plan (DEP).

## 12.2 Analysis Sets

### 12.2.1 Safety Analysis Set

Safety analyses will be conducted using the safety analysis set on a treatment-emergent basis. As such, the safety analysis set will include all subjects/eyes exposed to any study lenses evaluated in this study. [REDACTED]

[REDACTED], any AE or device deficiency occurring after informed consent and prior to the initial exposure to the study lenses (test or comparator) under evaluation in this clinical protocol will be listed as pretreatment.

For treatment-emergent safety analyses, subjects/eyes will be categorized under the actual study lenses exposed in the corresponding study lens sequence.

### 12.2.2 Full Analysis Set

The full analysis set (FAS) is the set of all randomized subjects who are exposed to any study lenses evaluated in this study, [REDACTED].

### 12.2.3 Per Protocol Analysis set

The per protocol (PP) analysis set is a subset of FAS and excludes all data/subjects that have met any of the critical deviation or evaluability criteria identified in the DEP.

## 12.3 Demographic and Baseline Characteristics

Demographic information will be summarized by lens sequence and overall. Frequencies and percentages will be presented for categorical variables such as sex, age group, race, and ethnicity. Number of observations, mean, SD, median, minimum, and maximum will be presented for continuous variables such as age.

## 12.4 Effectiveness Analyses

This study defines 1 primary effectiveness endpoint, [REDACTED]

[REDACTED] evaluations will use the FAS as the primary analysis set. [REDACTED]

[REDACTED]

[REDACTED]  
[REDACTED]  
[REDACTED]

All effectiveness analyses will be carried based on the randomization assignment.

### **12.4.1 Analysis of Primary Effectiveness Endpoint(s)**

The primary objective of this study is to demonstrate NI in VA at distance when wearing T30 MFfA lenses compared to ULTRA MFfA lenses, after 30 days of wear (Day 30).

The primary endpoint is binocular HC/HI VA at distance (4 m) at Day 30 with study lenses, collected on the logMAR scale.

#### **12.4.1.1 Statistical Hypotheses**

The null and alternative hypotheses are formulated in terms of the predefined margin of 0.05 for NI:

$$H_0: \mu_{(T)} - \mu_{(C)} \geq 0.05$$

$$H_a: \mu_{(T)} - \mu_{(C)} < 0.05$$

where  $\mu_{(T)}$  and  $\mu_{(C)}$  denote the mean distance binocular HC/HI VA at Day 30 for T30 MFfA and ULTRA MFfA, respectively, in logMAR scale.

### 12.4.1.2 Analysis Methods

A mixed effects repeated measures model will be utilized to test these hypotheses. The model will include terms for lens, visit, lens-by-visit interaction, period, and study lens sequence. Within-subject correlation due to crossover will also be accounted for in the model.

Lens difference (T30 MFFA minus ULTRA MFFA) and the corresponding one-sided 95% upper confidence limit (UCL) at Day 30 will be computed. Noninferiority will be declared if the UCL is less than 0.05.

## 12.5 Handling of Missing Data

All data obtained in evaluable subjects/eyes will be included in the analysis. No imputation for missing values will be carried out for effectiveness analyses.

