### 7.2 Rationale for Study Design

This study design is justified based upon an evaluation of the results of relevant preclinical and clinical testing, as described within the IB.

The bilateral, crossover study design will ensure that the same subject is exposed to both the test and comparator lens materials during the wearing period. Therefore, [REDACTED] [REDACTED] assessments can be obtained for both lenses from the same subject.

The study will include only those subjects who are successful wearers of soft multifocal contact lenses in both eyes during the past 3 months for a minimum of 5 days per week and 8 hours per day. This will avoid confounding safety responses in non-adapted subjects. Habitual ULTRA MFfA and ULTRA for Presbyopia contact lens wearers are allowed to participate in this trial and may constitute up to approximately 50% of the total subject population. The study will exclude subjects who are monovision contact lens wearers of contact lens in one eye only.

Lubrication/rewetting drops will not be permitted during study lens wear, as this may confound the primary effectiveness and key exploratory variables. However, habitual lubrication/rewetting drop usage is allowed up to 10 minutes prior to lens insertion and any time after lens removal during the study.

Currently pregnant or lactating women and participants with any history of amblyopia, strabismus or binocular vision abnormalities will be excluded from the trial, to prevent confounding the safety/effectiveness endpoints. Subjects who become pregnant during the study will not be discontinued; however, data will be excluded from the effectiveness analyses because pregnancy can alter refraction and VA results.

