## 8 STUDY POPULATION

The study population consists of male and female subjects 40 years old and above with a diagnosis of both presbyopia and astigmatism. It is aimed to enroll (consent) approximately 82 subjects in approximately 8 sites in the US, with a target of 74 total subjects completed, with approximately 10 (intended minimum) to 12 (intended maximum) subjects per site. Site-specific targets may vary based upon individual site capabilities. Estimated time needed to recruit subjects for the study is approximately 5 weeks; however, unanticipated circumstances may shorten or lengthen this time and would not require amendment of this protocol. Because an approximately 5% screening failure rate and 5% discontinue rate is expected, approximately 82 subjects are expected to be enrolled.

This protocol allows enrollment of the following vulnerable population(s), with associated justification for each population:

Elderly (age 65 years or above) – Presbyopia and associated gradual loss of accommodation is part of the aging process and worsens with increasing age. Multifocal contact lenses are a commonly used correction option for this condition. The contact lens under study is intended to alleviate this condition. Therefore, it is appropriate and necessary to include elderly subjects in this clinical trial to gain data regarding the safety and effectiveness of the T30 MFfA contact lenses in this population. Elderly subjects will be protected through the informed consent process, which will include any risks specific to the elderly subjects, as well as any specific responsibilities associated with their participation. In addition, an IRB/IEC will review and approve the inclusion of elderly subjects in this clinical trial prior to enrollment of elderly subjects. Any specific requirements imposed by the IRB/IEC regarding participation of elderly subjects will be implemented and documented, as appropriate. Upon conclusion of the clinical trial, all subjects, including elderly subjects, will return to standard medical care for ongoing conditions.

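### Does the reference to evaluable subjects in Section 12.5 bring per-protocol exclusions into the primary FAS analysis?

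*Protocol*

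**What the plan says.** Section 12.1 bases evaluability on the DEP and fixes its timing: "Final subject evaluability must be determined prior to breaking the code for masked treatment assignment and locking the database".

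Section 12.2.2 defines the FAS as the "set of all randomized subjects who are exposed to any study lenses evaluated in this study". A redacted clause follows the comma. Section 12.2.3 takes the PP set as a subset of the FAS that "excludes all data/subjects that have met any of the critical deviation or evaluability criteria identified in the DEP". Section 12.4, with redactions before and after, says that "evaluations will use the FAS as the primary analysis set".

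Section 12.5 has two sentences and no redaction. The first is "All data obtained in evaluable subjects/eyes will be included in the analysis". The second rules out imputation for effectiveness analyses.

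On pregnancy, Section 7.2 says "data will be excluded from the effectiveness analyses because pregnancy can alter refraction and VA results", and Section 11.7 says "data will be excluded from the effectiveness analysis because pregnancy can alter refraction and VA results". Neither gives a date from which the exclusion runs.

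**The concern.** Evaluability is a working term in this protocol. In the visible set definitions it appears only where the PP set is separated from the FAS. When Section 12.5 then admits evaluable subjects' data to an unnamed analysis, a strict reader could conclude that non-evaluable subjects also leave the primary FAS analysis.

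That would matter for three reasons.

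- Noninferiority is declared from one upper confidence limit against 0.05 logMAR (Section 12.4.1.2), and nothing is imputed, so the subjects analysed determine the estimate.
- Section 10.5.2 asks that subjects who stop study treatment stay in the study and continue assessments. Under the strict reading their data would count only if the DEP called them evaluable.
- Settling evaluability before unmasking prevents result-driven exclusion. It does not remove bias from exclusions that are themselves related to lens performance.

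The pregnancy sentences raise a similar question, because they remove data without naming a set or a starting time, and the visible FAS definition carries no matching exception.

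**Working it through.** **Setting the provisions side by side**

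| Section | What it governs | Use of evaluability |
|---|---|---|
| 12.1 | How and when evaluability is settled | Defined through the DEP, before unmasking |
| 12.2.2 (visible part) | Who is in the FAS | None: randomized and exposed |
| 12.2.3 | Who is in the PP set | Used, with critical deviations, to subtract from the FAS |
| 12.4 (visible part) | Which set is primary | None: the FAS |
| 12.5 | Missing data | Evaluable data go in; nothing is imputed |

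Section 12.5 is the only general statement here. It says that evaluable data are included. Excluding other FAS data needs a negative inference that the sentence does not make. Three specific provisions (12.2.2, 12.2.3 and 12.4) point the other way, and an analyst who follows them runs the primary model on randomized, exposed subjects. The reference to eyes also suggests wording written for endpoints in general, since the primary endpoint is binocular.

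**Enrolment figures (Section 8)**

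Section 8 states: "Because an approximately 5% screening failure rate and 5% discontinue rate is expected, approximately 82 subjects are expected to be enrolled". The completion target is 74.

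- Enrolment needed: 74 / (0.95 × 0.95) = 81.99, so 82, as stated.
- Forward: 82 × 0.95 = 77.9 randomized; 77.9 × 0.95 = 74.0 completed.

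The figures reproduce. They show no separate allowance for non-evaluable completers, but most of the sample-size section is not visible, so 74 may already hold a reserve.

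**Size of the effect if the strict reading were applied**

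The protocol gives no non-evaluable share, so the share f is an assumption. Completers left = 74 × (1 − f); standard error ratio = 1/√(1 − f).

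| Assumed f | Completers left | SE ratio |
|---|---|---|
| 2% | 72.5 | 1.010 |
| 5% | 70.3 | 1.026 |
| 10% | 66.6 | 1.054 |

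Shift in the estimate = (k/74) × d, where k is the number excluded and d is an assumed gap of 0.05 to 0.10 logMAR between the mean lens difference in excluded and in retained subjects.

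- k = 4: 4/74 × 0.05 = 0.003 and 4/74 × 0.10 = 0.005.
- k = 7: 7/74 × 0.05 = 0.005 and 7/74 × 0.10 = 0.009.

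Both compare with a margin of 0.05.

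Power = Φ(0.05/(SD/√n) − 1.645), with true difference 0 and an assumed paired SD:

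- SD 0.10: 99.6% at n = 74 and 99.3% at n = 67.
- SD 0.15: 88.9% at n = 74 and 86.1% at n = 67.

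**Pregnancy**

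Every subject is 40 or older, so 0 to 1 case is assumed: at most 1/74 = 1.4% of completers. Both sentences apply the exclusion to effectiveness analysis without qualification, which on a plain reading covers every effectiveness set. A definition of who belongs to the FAS can coexist with a stated exclusion of particular data. Only the starting time is unstated.

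**The case for a change.** The strongest case for a change is that the protocol should not use a defined term loosely. On the visible text evaluability has one function, separating PP from FAS, and Section 12.5 uses the same word without limiting it. Avoiding the strict reading means giving the word a broader sense that the protocol does not state. The DEP can say who is evaluable, but it is Section 12.5 that states the consequence, and that section is not redacted. In a noninferiority trial the FAS and PP analyses should remain distinct, and one added clause would remove the doubt at almost no cost.

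Part of this stands. Section 12.5 names no set, its wording is looser than that of the sections around it, and fixing evaluability before unmasking does not decide which set the sentence refers to. What does not stand is the step from loose wording to a wrongly run primary analysis. The FAS definition breaks off at a redacted clause, Section 12.4 is redacted on both sides of its FAS sentence, and the Glossary makes the DEP and the SAP part of the clinical investigation plan. Two analysts would reach different subject sets only if both worked without those documents and one let a general sentence override the set definitions. Nor would the two sets merge on the strict reading, because Section 12.2.3 also removes critical deviations and individual data.

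**Conclusion.** No change to the plan is called for. This is a gap in wording that an analyst following Sections 12.2.2, 12.2.3 and 12.4 fills correctly: the primary analysis uses the FAS, and DEP evaluability shapes the PP set. A clause naming the set would read better, but it would not alter any analysis that the visible text prescribes.

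The size under the less favourable reading is modest. The standard error rises by 1.0% to 5.4% for an assumed 2% to 10% non-evaluable share. The estimate shifts by at most about 0.009 logMAR with 7 of 74 excluded and an assumed gap of up to 0.10. These figures rest on assumed shares, gaps and SDs, because the protocol shows none of them; any actual bias cannot be computed. The enrolment figure of 82 reproduces. The missing starting time for the pregnancy exclusion concerns at most one subject on the assumption made, and is a detail for the DEP or SAP. Confining that exclusion to the PP set or to later measurements would be a preference, not a correction.

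The conclusion would need revisiting only if the redacted FAS clause, the DEP or the SAP applied evaluability to the FAS itself.
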